# OTHER DATA

Participant's socio-demographic data and surgery data will be collected, including age, gender, marital status, education level, occupation, and type of surgery, type and dose of anaesthetic and previous surgeries. This data will be collected from the participant's health record by the PhD candidate.

## BLINDING

The Research Assistant involved in outcome data collection will be blinded to the group allocation, as will the statistician who will conduct the analysis. Clinicians (nurses, doctors, and other healt h providers) will not be told who is participating in the study nor their group allocation; however, it is acknowledged that it is not possible to prevent participants from sharing this information with them.

# SAMPLE SIZE

Based on the previous study of Bekelis et al. (2017), a sample of 150 participants (75 per group) will give the study 80% power to detect a moderate effect size of 0.5 standard deviations between groups in the primary outcome variable, with a type 1 error rate of 5%. This calculation assumes a dropout rate of 15%.

# STATISTICAL PLAN

Characteristics of groups will be summarised using counts and percentages for categorical variables and means and standard deviations for continuous variables. The primary outcome will be compared between groups at each follow-up time points using a linear mixed effects regression model, with fixed effects including treatment arm time (categorical), the interaction between treatment and time, and the baseline value of the outcome variable. Differences in mean VAS anxiety scores

between groups at each time point will be presented together with 95% confidence intervals and pvalue. Continuous secondary outcomes with repeated measurements will be compared using the same model. Hospital length of stay will be compared using the rank-sum test. Patient satisfaction and the VRSQ will be compared between groups using an independent sample t-test.

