# **PRIMARY OUTCOME**

Perioperative anxiety as measured by the visual analog scale for anxiety (VAS-A).

The visual analog scale for anxiety (VAS-A) is valid, reliable, and frequently used for evaluation of perioperative anxiety that allows detection of high anxiety levels in the various surgical group

(Kindler, Harms, Amsler, Ihde-Scholl, & Scheidegger, 2000). The VAS-A consists of a 100 mm horizontal line that represents two behavioral extremes at either end of the continuum (i.e., 'not at all anxious' = 0, whereas 'extremely anxious' = 100). Potential participants will be asked to rate their level of anxiety on the VAS-A tool at three-time points in the study. On admission to the preoperative area (T1), immediately before surgery (T2), and one hour after surgery (T3). Scores on the VAS-A of 25 or higher are said to reflect significant levels of anxiety (Kindler et al., 2000). The primary outcome will be collected by a Research Assistant at the research site, King Abdulaziz University Hospital.

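### VAS-A is tested separately at T2 and T3 with no primary time point or success rule, so the single-comparison 5% error and 80% power do not describe the planned primary analysis

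*Protocol*

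**What the plan says.** The Primary Outcome section defines the outcome as perioperative anxiety on the VAS-A, rated at three times: "On admission to the preoperative area (T1), immediately before surgery (T2), and one hour after surgery (T3"). It does not single out any of them. The Hypothesis predicts a 20-point reduction and names no time. The schedule under Summary of Outcomes marks T2 and T3 alike for the primary outcome.

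The Statistical Plan then fixes the comparison: "The primary outcome will be compared between groups at each follow-up time points using a linear mixed effects regression model". The fixed effects are arm, time, their interaction and the baseline value. The differences in mean score "between groups at each time point will be presented together with 95% confidence intervals and pvalue".

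The Sample Size section states that recruiting 75 patients to each arm, 150 in all, "will give the study 80% power to detect a moderate effect size of 0.5 standard deviations between groups". That figure refers to VAS-A. The error level is given once, for the whole calculation: "with a type 1 error rate of 5" per cent. Dropout is allowed for at 15%. This section too names no time point. No hierarchy, joint test, adjustment or success rule appears anywhere in the protocol.

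**The concern.** One hypothesis is served by two p-values, and the text does not say which p-value, or what combination of them, settles it. The error rate and power are stated as though there were one test.

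Two things are at stake. The first is whether the stated 5% and 80% are true of the decision the trial will make. The second is whether the deciding time point could be picked once results are known. T2 and T3 answer different questions: anxiety just before surgery, shortly after VR, and anxiety one hour after surgery.

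**Working it through.** **Inputs from the protocol.** Effect 0.5 SD; type 1 error 5% (taken as two-sided, in line with the 95% confidence intervals); power 80%; 75 per group; dropout 15%; allocation 1:1; two follow-up time points.

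**Input not in the protocol.** The correlation ρ between the T2 and T3 test statistics. It is treated as an assumption and varied.

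**1. The plan's own figure.**
- n per group = 2(1.960 + 0.842)² / 0.5² = 62.8, rounded up to 63.
- Inflated for dropout: 63 / 0.85 = 74.1, rounded up to 75 per group, or 150 in total.

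The stated size reproduces for exactly one two-sided 5% comparison.

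**2. Success if either time point is significant.** Familywise error = 1 − P(|Z₁| < 1.96 and |Z₂| < 1.96), with (Z₁, Z₂) bivariate normal with correlation ρ. At ρ = 0 this is 1 − 0.95² = 0.0975.

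| ρ | Familywise error |
|---|---|
| 0 | 9.75% |
| 0.3 | 9.51% |
| 0.5 | 9.07% |
| 0.7 | 8.35% |
| 0.8 | 7.81% |
| 0.9 | 7.04% |

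**3. Success only if both are significant.** The error cannot exceed 5%, because each test alone is held at 5%. For power, take 75 × 0.85 = 63.75 completers per group and an effect of 0.5 SD at both times.
- Noncentrality = 0.5 × √(63.75 / 2) = 2.823.
- Power of one test = Φ(2.823 − 1.960) = Φ(0.863) = 80.6%.
- Power for both = P(Z₁ < 0.863 and Z₂ < 0.863): 67.5% at ρ = 0.3, 69.5% at 0.5, 72.1% at 0.7.

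These figures are unadjusted for baseline, like the calculation in step 1.

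**4. Effect of the planned baseline adjustment.** With baseline–outcome correlation r (not given; assumed), the noncentrality becomes 2.823 / √(1 − r²). At r = 0.43 it is 2.823 / 0.903 = 3.127.
- Power of one test = Φ(3.127 − 1.960) = 87.8%.
- Power for both is then about 79% at ρ = 0.3 and 82% at ρ = 0.7.

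The loss in step 3 therefore belongs to the calculation as the protocol presents it. Baseline adjustment might recover it, but the protocol does not claim or quantify that.

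**The case against.** The strongest reply is that the protocol never says the trial succeeds if either time point is significant. It says only that the differences will be presented. If both were required, or one joint test decided, the error would not exceed 5%. This stands. A reader might infer that the trial's true type 1 error is 8% to 10%, but the documents do not support that as a fact. It needs the unwritten either-time-point rule and a correlation of no more than about 0.77; at 0.9 the figure is 7.0%. The 5% is correct for each test taken singly.

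A reader might also infer that splitting alpha between the time points must cost a good deal of power. An unadjusted calculation does suggest so, but the planned model adjusts for baseline. At a baseline–outcome correlation of about 0.43, power at 2.5% per test is back to about 80%, so no firm loss can be claimed. Nor do the documents give any figure to show that T3 ratings would be less obtainable than T2 ratings.

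Further, multiplicity rules are often left to a statistical analysis plan, the analysing statistician is blinded, and both results are to be reported. These points limit selective emphasis but do not remove it. The time point that defines the primary outcome belongs with the outcome definition and the sample size, and both are in this protocol. The protocol is also not silent on the analysis: it fixes the model, the two comparisons and a p-value for each.

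**Conclusion.** The concern holds as a mismatch between the planned analysis and the stated design properties. Under either per-time-point rule, the Sample Size section does not describe the decision:

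- **Either significant:** error of about 7% to 9.75% for assumed ρ from 0.9 to 0, against a stated 5%.
- **Both required:** error at or below 5%, but power of about 67% to 72% for assumed ρ of 0.3 to 0.7, against a stated 80%. This assumes 0.5 SD at both times and no baseline adjustment.

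Of the per-time-point readings, only a single named time point agrees with the sample size as calculated. That no primary time point or success rule is given is certain from the text. The size of the consequence depends on the rule adopted and on correlations the protocol does not give.

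**What to change.** Pre-specify one primary contrast from the planned mixed model, tested at two-sided 5%. Two choices are sound, and the sponsor should pick one:

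- **Treatment difference at T2**, with T3 tested only if T2 is significant and otherwise descriptive. T2 is the natural default because VR is given in the preoperative holding area and the schedule places exposure at that point. The sample size of 150 stands as calculated.
- **One treatment contrast averaged over T2 and T3**, if the claim is to keep its perioperative scope. It also holds 5%, but the sample size should be restated for it, because power then depends on the T3 effect and on ρ. For example, take 63.75 completers per group, ρ = 0.5 and no baseline adjustment, so that the average has an SD of √0.75 = 0.866. An effect of 0.5 SD at both times gives Φ(0.5 / 0.866 × 5.646 − 1.960), about 90%. If the T3 effect is half as large, the average effect is 0.375 SD and power is about 69%.

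State the same choice in the Hypothesis, Primary Outcome, Sample Size and Statistical Plan sections. Data collection does not change. For the T2 option the cost is wording, plus a narrower primary claim: T3 can no longer support it alone. For the averaged option, neither time point can do so alone.

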### RANDOMISATION

Participants will be randomly allocated to intervention or control via block randomisation on a 1:1 ratio (control: intervention) using a computerised random number sequence created by an independent statistician. In addition, randomisation will be stratified by surgery type (i.e., general surgery, neurosurgery, cardiac surgery, thoracic surgery, and orthopedic surgery).

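### Randomisation is stratified by surgery type, but the planned analyses do not name it; precision is lost to the extent that surgery type predicts the outcome

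*Protocol*

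**What the plan says.** The Randomisation section of the Protocol uses "block randomisation on a 1:1 ratio (control: intervention" and adds that "randomisation will be stratified by surgery type (i.e., general surgery, neurosurgery, cardiac surgery, thoracic surgery, and orthopedic surgery". Block size is not given. The Other Data section records type of surgery for every participant, so the variable will be in the dataset.

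The Statistical Plan then sets the between-group analyses:

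- Primary outcome (VAS-A): a linear mixed model "with fixed effects including treatment arm time (categorical), the interaction between treatment and time, and the baseline value of the outcome variable".
- Repeated secondary outcomes: "Continuous secondary outcomes with repeated measurements will be compared using the same model".
- Length of stay: "Hospital length of stay will be compared using the rank-sum test".
- Satisfaction: "Patient satisfaction and the VRSQ will be compared between groups using an independent sample t-test".

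Surgery type appears in none of these.

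**The concern.** Stratified blocks hold the arms nearly balanced on surgery type. Differences between surgery types then contribute almost nothing to the sampling error of the treatment difference. An analysis that ignores the strata still counts those differences as noise, so its standard error describes a less balanced trial than the one that was run. Confidence intervals come out too wide, p-values too large, and the actual type 1 error falls below the stated 5%.

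What is at stake is precision that the design has already secured. Length of stay and satisfaction are the most exposed by construction, because their tests carry no covariate at all. The mixed model has the baseline value, which may already absorb part of any difference between surgery types.

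**Working it through.** **1. The plan's own sample size.** Inputs from the Sample Size section: 0.5 SD, 80% power, 5% type 1 error (taken as two-sided), 15% dropout.

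n per group = 2 x (1.96 + 0.8416)^2 / 0.5^2 = 62.8, so 63. Allowing for dropout, 63 / 0.85 = 74.1, so 75 per group and 150 in total. The stated figure reproduces, and it does not rely on any gain from stratification.

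**2. Size of the standard-error mismatch.** Take outcome variance 1 (after baseline, where the model has it), of which surgery type explains R2.

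- Reported variance of the difference, strata ignored: 2/n.
- Actual variance with balanced strata: about 2(1 - R2)/n.
- Ratio of reported to actual standard error: 1/sqrt(1 - R2).

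At n = 63 and R2 = 0.20, the reported SE is sqrt(2/63) = 0.178, the actual SE is 0.178 x sqrt(0.80) = 0.159, and the ratio is 1.118. The actual type 1 error is then about 2 x Phi(-1.96 x 1.118) = 2.8%.

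**3. Simulation, continuous outcome.** Five equal strata, blocks of 4 (assumed), 63 completers per group, effect 0.5 SD, 4000 runs per setting, one follow-up time point. The Protocol gives no R2, so a range is shown.

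| Assumed R2 | SE too large by | Power without / with strata | Type 1 error without / with strata |
|---|---|---|---|
| 0 | 0% | 80% / 80% | 5.1% / 5.1% |
| 0.05 | 3% | 80% / 82% | 4.8% / 5.2% |
| 0.10 | 5% | 80% / 83% | 3.7% / 4.6% |
| 0.20 | 12% | 82% / 88% | 2.9% / 4.8% |
| 0.40 | 29% | 85% / 94% | 1.6% / 5.1% |

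An assumed unequal mix of strata gives similar results; at R2 = 0.20, for example, power is 82% versus 87%. Monte Carlo error on a power near 80% is sqrt(0.8 x 0.2 / 4000), about 0.6 points.

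**4. Simulation, length of stay.** Whole days, 126 completers, log-SD 0.5, stay ratio 0.77, 3000 runs per setting; all are assumptions except the whole-day scale. The plain rank-sum test is compared with the stratified rank-sum (van Elteren) test.

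| Assumed stratum medians (days) | Mix | Power, plain / stratified | Type 1 error, plain / stratified |
|---|---|---|---|
| all 3 | equal | 79% / 78% | 4.5% / 4.7% |
| 2.5 to 4 | equal | 75% / 76% | 4.7% / 5.5% |
| 2 to 7 | equal | 60% / 79% | 1.3% / 4.4% |
| 2 to 7 | unequal | 49% / 78% | 0.6% / 4.7% |
| 2 to 9 | equal | 48% / 80% | 0.8% / 4.5% |
| 2 to 9 | unequal | 41% / 76% | 0.5% / 4.9% |

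The gap runs from about zero (the plain test is marginally ahead when strata do not differ) to between 19 and 35 points when the medians are widely spread.

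**The case against.** - **The mixed model may not be closed.** The Statistical Plan introduces its fixed effects as a list that need not be complete, and a separate analysis plan may add surgery type. This stands in part: one cannot say that the primary analysis will certainly omit the factor. It does not help length of stay or satisfaction, where the named tests have no place for a stratum.
- **The loss is conditional.** Nothing in the Protocol says how strongly surgery type predicts any outcome. Only the part left after baseline matters in the mixed model. T2 precedes the operation, and screening to APAIS 11 or more may narrow differences between surgery types. The simulation also has no repeated measures or explicit baseline term. All of this stands, so the figures are a range and not a prediction.
- **The trial is not underpowered.** A reader might infer that ignoring the strata undercuts the 80% power or makes 150 too few. It does not: power without strata was about 80% or more in every row for the continuous outcome. The loss is relative to what the design could deliver.
- **No false positives follow.** A reader might also infer an inflated type 1 error. The direction is the opposite.
- **Length of stay as the main casualty.** It is tempting to state a large loss there as a fact. The stratum medians and the treatment effect are assumed, and the Protocol makes no power claim for stay. The documents support only the conditional statement.
- **The VRSQ.** The Statistical Plan puts it in the same t-test sentence, but only the intervention group completes it, so it lies outside this point.

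**Conclusion.** The mismatch between design and analysis is real. It is firm for length of stay and satisfaction, and for the mixed model it holds as the Protocol is now worded. Its effect is conservative and depends on R2: for R2 of 0 to 20% the standard errors are 0 to 12% too large and power is 0 to 6 points lower than in a stratified analysis. For length of stay the loss ranges from about zero to 35 points over the scenarios tried.

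These sizes rest on assumed R2, stratum medians, strata mix and a block size of 4. The validity of the trial and its sample size are not in question. The change is still worth making because it costs almost nothing if surgery type turns out not to matter (80% versus 80% power; 79% versus 78% for stay) and may recover a good deal if it does.

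**What to change.** In the Statistical Plan, before unblinding:

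1. Add surgery type, as used for randomisation, as a fixed effect in the mixed model for VAS-A and for the repeated secondary outcomes.
2. Replace the rank-sum test for length of stay with the stratified rank-sum (van Elteren) test.
3. Replace the t-test for satisfaction with a linear model on arm plus surgery type.
4. State a rule for pooling sparse strata, fixed without reference to arm. Also state which stratum takes surgery types outside the five listed. Eligibility covers any elective surgery except dental, and Study Setting names ENT, plastic, vascular and other specialties that have no stratum.

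The data are already to be collected and N does not change. The cost is a short edit, including the pooling rule, and 5 - 1 = 4 degrees of freedom. In a simple comparison of 126 completers that means 120 instead of 124.

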### SECREEING

Patients who meet the above inclusion criteria will be screened for their anxiety level using a validated tool which is The Amsterdam Preoperative Anxiety and Information score (APAIS) (Boker et al., 2002; Laufenberg-Feldmann & Kappis, 2013). The PhD candidate will apply the Amsterdam Preoperative Anxiety and Information score (APAIS) on the day of their surgery in the preoperative holding area. Patients with moderate to high level of preoperative anxiety - defined as a preoperative anxiety score ≥11 (Song et al., 2019) - will be included.

The APAIS is a rapid and clinically practical assessment tool developed by Nelly Moerman and previously validated against other scales to evaluate patients' preoperative anxiety with good sensitivity and strong specificity for clinically significant anxiety (Boker et al., 2002; Laufenberg-Feldmann & Kappis, 2013). It consists of six questions in total. Each question is rated on a five-point Likert scale from 1: "not at all" to 5: "extremely". The sum of scores from questions 1, 2, 4, and 5

show the anxiety level. The sum of scores from questions 3 and 6 show the level of information required by each individual regarding the anesthesia and surgical procedure. A patient with a score of 11 or more (scoring range from 4 to 20) on the anxiety scale experiences moderate to severe anxiety requiring further intervention (Berth, Petrowski, & Balck, 2007; Boker et al., 2002; Laufenberg-Feldmann & Kappis, 2013). On the need for information scale, patients scoring 2 – 4 are categorised as having little and no need for information, patients scoring 5 – 7 are categorised as having an average need for information and the patients scoring 8 – 10 are considered as having high need for information(Berth et al., 2007; Laufenberg-Feldmann & Kappis, 2013).

Amsterdam Preoperative Anxiety and Information score (APAIS)(Berth et al., 2007):

Questions:	1	2	3	4	5
1- I am worried about the anesthetic					
2- The anesthetic is on my mind continually					
3-I would like to know as much as possible about the anesthetic					
4- I am worried about the procedure					
5-The procedure is on my mind continually					
6- I would like to know as much as possible about the procedure					

1:Not at all, .2:Somewhat, 3:Moderate, 4: Moderately high, 5:Extremely

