### ALLOCATION CONCEALMENT

Sealed opaque envelopes organised in numbered sequential order will be used to conceal the treatment allocation. Following screening, potential participants with moderate to high levels of

anxiety will be allocated to the treatment group (either intervention or control) contained in the next envelope.

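### Satisfaction is tested without any covariate although every randomised patient has a pre-allocation anxiety score (APAIS): a small missed efficiency, not an error

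*Protocol*

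**What the plan says.** **When APAIS is taken.** Under Screening: "The PhD candidate will apply the Amsterdam Preoperative Anxiety and Information score (APAIS) on the day of their surgery in the preoperative holding area". The anxiety score is the sum of four items (range 4 to 20), and 11 or more is needed for entry. Under Allocation Concealment, the next envelope is used only once screening is done: "Following screening, potential participants with moderate to high levels of" anxiety are then allocated. The schedule table lists the APAIS screen and allocation together at t0, and the first VAS-A at t1.

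**What the analyses use.** Under Statistical Plan, the VAS-A mixed model has "fixed effects including treatment arm time (categorical), the interaction between treatment and time, and the baseline value of the outcome variable". For satisfaction: "Patient satisfaction and the VRSQ will be compared between groups using an independent sample t-test". No analysis in that section mentions APAIS.

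**Satisfaction.** The LPPSq is completed once, at T4 (24 hours after surgery, before discharge). It has 39 items in six dimensions (4 + 7 + 7 + 4 + 14 + 3), and one seven-item dimension concerns fear.

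**The concern.** A covariate measured before allocation, complete by design and plausibly related to the outcome can be adjusted for in a randomised comparison without material bias, and it narrows the confidence interval in proportion to how well it predicts. APAIS meets the first two conditions, because nobody can be randomised without it. The plan uses it only as a gate.

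The point bites hardest on satisfaction. That outcome has no baseline value and no other covariate, and the protocol names the test outright, so an analysis that follows the text leaves APAIS out. Adding it after unblinding would look data-driven. For VAS-A there is less to gain, because the model already carries the T1 value of the same construct. What is at stake is precision only, not validity.

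**Working it through.** **1. The plan's own figure.** Inputs from Sample Size: "80% power to detect a moderate effect size of 0.5 standard deviations between groups in the primary outcome variable", type I error 5% (two-sided taken, since sidedness is not stated), 15% dropout.

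- Per arm: 2 × (1.960 + 0.842)² / 0.5² = 62.8, so 63.
- With dropout: 63 / 0.85 = 74.1, so 75 per arm and 150 in total, as stated.

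This is an unadjusted two-sample calculation. Leaving APAIS out therefore does not take power below the stated 80%.

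**2. What the entry cut-off does to the correlation.** Only scores of 11 to 20 are randomised. Assume the unselected score has mean 9 to 11 and SD 4 (not in the documents). The SD among those who enter is then about u = 0.6 of its unselected value. An unselected correlation R becomes

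r = R·u / √(1 − R² + R²u²).

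With u = 0.6, R = 0.3 gives 0.19, R = 0.4 gives 0.25 and R = 0.5 gives 0.33. I take r = 0.1 to 0.33 as the working range.

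**3. Satisfaction: t-test against regression on arm and APAIS.** The residual variance is multiplied by 1 − r², the standard error by √(1 − r²), and the standardised effect becomes 0.5/√(1 − r²). Evaluable patients per arm: 75 × 0.85 = 63.75, taken as 64. Power is from the non-central t distribution. The 0.5 SD is borrowed from the primary outcome, because the protocol sets no target for satisfaction.

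| r (assumed) | 1 − r² | SE falls by | Effect in residual SD | Power |
|---|---|---|---|---|
| 0 | 1.000 | 0% | 0.500 | 80.1% |
| 0.1 | 0.990 | 0.5% | 0.503 | 80.5% |
| 0.2 | 0.960 | 2.0% | 0.510 | 81.7% |
| 0.3 | 0.910 | 4.6% | 0.524 | 83.7% |
| 0.33 | 0.891 | 5.6% | 0.530 | 84.5% |

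Going from 126 to 125 residual degrees of freedom changes these powers by less than 0.1 percentage point.

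**4. VAS-A: APAIS added to a model that already has T1 VAS-A.** Treat one follow-up time as a linear model. Let r₁ be the correlation of T1 with follow-up, rₐ that of APAIS with follow-up, and rₓ that of T1 with APAIS. Then

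R² = (r₁² + rₐ² − 2·r₁·rₐ·rₓ) / (1 − rₓ²),

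and the residual variance is multiplied by (1 − R²)/(1 − r₁²). Assumed ranges: r₁ 0.4–0.6, rₐ 0.25–0.45, rₓ 0.3–0.5.

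- Least gain, (0.5, 0.25, 0.5): R² = (0.25 + 0.0625 − 0.125)/0.75 = 0.25, the same as T1 alone. Gain zero.
- Most gain, (0.4, 0.45, 0.3): R² = (0.16 + 0.2025 − 0.108)/0.91 = 0.280. The variance factor is 0.720/0.84 = 0.858, so variance falls 14.2% and the standard error 7.4%.
- Median over a grid in steps of 0.05: variance falls 3.6%, standard error 1.8%.

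**The case against.** **Precision covariates usually belong in the SAP.** The word including in the description of the mixed model leaves room for more terms. For VAS-A this stands, so APAIS there is only an option. It does not dispose of satisfaction, where the protocol fixes a specific test that takes no covariate.

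**Nothing planned is invalid.** This stands in full. A reader might infer that the trial is underpowered or its estimates biased because APAIS is unused. The documents support neither: the 150 comes from an unadjusted calculation, and a t-test in a randomised comparison is sound.

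**Nothing shows that APAIS predicts satisfaction.** True. Only 7 of the 39 items concern fear; the other 32 cover information, discomfort, competence, staff relationship and service. With r = 0 the gain is nil. A reader might also hope for 90% power, or the equivalent of a third more patients. That needs r = 0.5 among those randomised, since 1/(1 − 0.25) = 1.33, which under the u = 0.6 assumption requires an unselected correlation of about 0.69. Nothing in the documents points that high.

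**Why APAIS rather than age, previous surgery or type of surgery, which are also collected?** The documents do not show that it is the strongest predictor. Its claim is practical: entry guarantees that it is complete, it precedes allocation, and it measures what the intervention targets.

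**Two further readings go too far.** Because the schedule puts VAS-A at t1, after allocation at t0, one might say APAIS repairs the baseline. It does not; it is only the one anxiety measure that the schedule clearly places before allocation. Nor is there a case for adding APAIS to the cortisol, heart-rate and pain models: they carry their own T1 values, and nothing here suggests a gain.

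**Conclusion.** The point holds as a modest, nearly free improvement to the satisfaction comparison. If APAIS correlates 0.1 to 0.33 with satisfaction among patients scoring 11 or more, the standard error falls by about 0.5% to 6%, and power for 0.5 SD at 64 per arm moves from about 80% to 80.5%–84.5%. These figures rest on assumed correlations, an assumed APAIS distribution before selection, and an effect size that the protocol states only for the primary outcome.

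For VAS-A, the further fall in standard error is 0% to 7.4% over the assumed correlations, typically about 2%, and may be nothing. A reader should not infer a definite loss of precision in the primary analysis. The sample size and the validity of the planned analyses are unaffected. The VRSQ, named in the same sentence as satisfaction, is completed only in the intervention group and is not part of this point.

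**What to change.** In the Statistical Plan, replace the t-test for satisfaction with a linear regression of each reported satisfaction score on treatment arm and the screening APAIS anxiety score (sum of items 1, 2, 4 and 5, as a continuous covariate). Report the adjusted difference with its 95% confidence interval.

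Optionally, state that the same APAIS score enters the VAS-A mixed model alongside the T1 value, making no claim of a particular gain. Leave the cortisol, heart-rate and pain models as they are.

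Make the change before any unblinded data are seen. The cost is one or two sentences, no new data collection, and one degree of freedom of about 126 in the satisfaction analysis.
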